6.0 TRIAL PROCEDURES

6.1 Trial Procedures

The Trial Flow Chart – Section 5.0 summarizes the trial procedures to be performed at each visit. Individual trial procedures are described in detail below. It may be necessary to perform these procedures at unscheduled time points if deemed clinically necessary by the investigator.

Furthermore, additional evaluations/testing may be deemed necessary by the Sponsor and/or Merck for reasons related to subject safety. In some cases, such evaluation/testing may be potentially sensitive in nature (e.g., HIV, Hepatitis C, etc.), and thus local regulations may require that additional informed consent be obtained from the subject. In these cases, such evaluations/testing will be performed in accordance with those regulations.

6.1.1 Administrative Procedures

6.1.1.1 Informed Consent

The Investigator must obtain documented consent from each potential subject prior to participating in a clinical trial.

6.1.2.8 General Informed Consent

Consent must be documented by the subject's dated signature or by the subject's legally acceptable representative's dated signature on a consent form along with the dated signature of the person conducting the consent discussion.

A copy of the signed and dated consent form should be given to the subject before participation in the trial.

The initial informed consent form, any subsequent revised written informed consent form and any written information provided to the subject must receive the IRB/ERC's approval/favorable opinion in advance of use. The subject or his/her legally acceptable representative should be informed in a timely manner if new information becomes available that may be relevant to the subject's willingness to continue participation in the trial. The communication of this information will be provided and documented via a revised consent form or addendum to the original consent form that captures the subject's dated signature or by the subject's legally acceptable representative's dated signature.

Specifics about a trial and the trial population will be added to the consent form template at the protocol level.

The informed consent will adhere to IRB/ERC requirements, applicable laws and regulations and Sponsor requirements.

6.1.1.3 Inclusion/Exclusion Criteria

All inclusion and exclusion criteria will be reviewed by the investigator or qualified designee to ensure that the subject qualifies for the trial.

6.1.1.4 Medical History

A medical history will be obtained by the investigator or qualified designee. Medical history will include all active conditions, and any condition diagnosed within the prior 10 years that are considered to be clinically significant by the Investigator. Details regarding the disease for which the subject has enrolled in this study will be recorded separately and not listed as medical history.

6.1.1.5 Prior and Concomitant Medications Review

6.1.1.5.1 Prior Medications

The investigator or qualified designee will review prior medication use, including any protocol-specified washout requirement, and record prior medication taken by the subject within 28 days before starting the trial. Treatment for the disease for which the subject has enrolled in this study will be recorded separately and not listed as a prior medication.

6.1.1.5.2 Concomitant Medications

The investigator or qualified designee will record medication, if any, taken by the subject during the trial. All medications related to reportable SAEs and ECIs should be recorded as defined in Section 7.2.

6.1.1.6 Disease Details and Treatments

6.1.1.6.1 Disease Details

The investigator or qualified designee will obtain prior and current details regarding disease status.

6.1.1.6.2 Prior Treatment Details

The investigator or qualified designee will review all prior cancer treatments including systemic treatments, radiation and surgeries.

6.1.1.6.3 Subsequent Anti-Cancer Therapy Status

The investigator or qualified designee will review all new anti-neoplastic therapy initiated after the last dose of trial treatment. If a subject initiates a new anti-cancer therapy within 30 days after the last dose of trial treatment, the end-of treatment visit must occur before the first dose of the new therapy. Once new anti-cancer therapy has been initiated the subject will move into survival follow-up.

6.1.1.7 Assignment of Screening Number

All consented subjects will be given a unique screening number that will be used to identify the subject. Each subject will be assigned only one screening number. Screening numbers must not be re-used by different subjects.

Any subject who is screened multiple times will retain the original screening number assigned at the initial screening visit.

Specific details on the screening visit requirements (screening/rescreening) are provided in section 6.2.5.3.

6.1.1.8 Assignment of Treatment Number

All eligible subjects will be allocated by non-random assignment, and will receive a treatment allocation number. The allocation number identifies the subject for all procedures occurring after treatment allocation. Once an allocation number is assigned to a subject, it can never be re-assigned to another subject. A single subject cannot be assigned more than one allocation number.

6.1.1.9 Trial Compliance (Medication/Diet/Activity/Other)

Interruptions from the protocol-specified treatment for greater than 12 weeks between pembrolizumab doses due to non-drug-related or administrative reasons require consultation between the investigator and the Sponsor and written documentation of the collaborative decision on subject management.

The total volume of pembrolizumab infused will be compared to the total volume prepared to determine compliance with each dose of pembrolizumab administered. The instructions for the preparing and administering of pembrolizumab are provided in the Pharmacy Manual.

6.1.2 Clinical Procedures/Assessments

6.1.2.1 Adverse Event (AE) Monitoring

The investigator or qualified designee will assess each subject to evaluate for potential new or worsening Aes as specified in the Trial Flow Chart and more frequently if clinically indicated. Adverse experiences will be graded and recorded throughout the study and during the follow-up period according to NCI CTCAE Version 4.0. Toxicities will be characterized in terms regarding seriousness, causality, toxicity grading, and action taken with regard to trial treatment.

Please refer to section 6.2 for detailed information regarding the assessment and recording of Aes.

6.1.2.2 Full Physical Exam

The investigator or qualified designee will perform a complete physical exam during the screening period. Clinically significant abnormal findings should be recorded as medical history. A full physical exam should be performed during screening,

6.1.2.3 Directed Physical Exam

For cycles that do not require a full physical exam per the Trial Flow Chart, the investigator or qualified designee will perform a directed physical exam as clinically indicated prior to trial treatment administration.

6.1.2.4 Vital Signs

The investigator or qualified designee will take vital signs at screening, prior to the administration of each dose of trial treatment and at treatment discontinuation as specified in the Trial Flow Chart (Section 6.0). Vital signs should include temperature, pulse, respiratory rate, weight and blood pressure. Height will be measured at screening only.

6.1.2.5 Eastern Cooperative Oncology Group (ECOG) Performance Scale

The investigator or qualified designee will assess ECOG status (see Section 10.1) at screening, prior to the administration of each dose of trial treatment and discontinuation of trial treatment as specified in the Trial Flow Chart.

6.1.2.6 Post-study Anti-Cancer Therapy Status

The investigator or qualified designee will review all the new anti-cancer therapy initiated after the last dose of trial treatment. If a subject initiates a new anti-cancer therapy within 30 days after the last dose of trial treatment, the 30 day Safety Follow-up visit must occur before the first dose of the new therapy.

6.1.2.7 Tumor Imaging and Assessment of Response

Evaluation of response will include an evaluation of neurologic signs and symptoms (normal, improved, stable, deteriorated), CSF obtained from a previous positive site (lumbar or ventricular), and repeated radiologic evaluation of all ancillary studies (MRI Brain and Total spine with gadolinium contrast enhancement and CT scans of the body). Patients will be evaluated for CNS response based on a 4-point scale: complete response, improvement, stable disease and progression, as detailed in the Table below:

Table 8: Determination of Response to LMD

Clinical Assessment (Neurologic Function)	Size of LMD disease on MRI or CSF cytology	Overall Response Determination
No neurologic symptoms	None detectable	Complete response

Improved	Stable	Improved
Stable	Improved	Improved
Stable	Stable	Stable
Improved	Progression	Progression
Stable	Progression	Progression
Progression	Improved or Stable	Progression

We will define a positive CSF cytology result either detectable malignant cells in the CSF, or a pathology read that is reported as "suspicious for malignancy." We will define a negative CSF cytology result as either no detectable malignant cells in CSF, or a pathology read of "abnormal CSF cytology response," which will indicate conversion from positive/suspicious to negative/abnormal CSF cytology^{31,32}.

A complete responder will be defined as a patient with a normal neurologic examination, negative CSF cytology and no measurable leptomeningeal masses on radiologic imaging. Improved patients will be defined as those that have demonstrated improvement in neurologic signs or symptoms and/or a 50% decrease in CSF tumor cells or persistent positive CSF cytology as defined above, a 50% shrinkage in the bidirectional measurements of leptomeningeal disease. Patients with stable disease will be defined as less than 50% improvement in number of CSF tumor cells or abnormal CSF cytology response as defined above, or reduction in size of LMD on radiologic assessment, without evidence of progression. Progression will be defined as more than 25% increase in the number of tumor cells or persistent positive CSF cytology as defined above, an increase in size of LMD masses on radiologic assessment, or the development of new neurologic signs or symptoms after at least 2 cycles of pembrolizumab therapy.

Tumor imaging should be performed by computed tomography (CT) for body imaging (preferred) and for the CNS, gadolinium-enhanced MRI imaging of the brain and total spine including T1- weighted, T2-weighted, fluid attenuated inversion recovery and post-gadolinium sequences. The same imaging technique should be used throughout the trial. CT imaging should include the chest, abdomen and pelvis at baseline and all subsequent follow-up timepoints, additional details are in the Site Imaging Manual (SIM).

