4.1.5.1 Efficacy Endpoints

4.1.5.1.1 Primary Endpoint:

The primary efficacy endpoint is to evaluate CNS response with pembrolizumab in patients with LMD from solid tumors. CNS response will be defined either as radiologic response, cytologic response, or clinical response, whichever is easier to assess. Radiologic response will be defined as a reduction in size of a measurable lesion on a contrast-enhanced MRI scan of the brain. Cytologic response will be defined as a negative CSF cytology result in 2 consecutive samples, in patients who have initial positive cytology prior to treatment, or a clinical response, defined as an improvement in objective neurologic signs or symptoms attributable to LMD (Table 8). Response assessment is detailed in section 6.1.2.7.

4.1.5.1.2 Secondary Endpoints:

- **1. CNS Progression-free Survival:** A secondary endpoint of this study is to evaluate CNS-PFS, which will be defined as the time from study enrollment until CNS progression (radiologic, cytologic or clinical), or death, whichever occurs first. CNS progression will be classified as radiologic (determined by contrast-enhanced MRI scan), cytologic (determined by pathologic assessment of CSF cytology including cell count, differential, glucose) or clinical progression (defined as new objective neurologic signs or symptoms, attributable to LMD), as detailed in section 6.1.2.7.
- 2. **Overall Survival:** A secondary endpoint of this study is to evaluate OS, which will be defined as the time from study enrollment until death from any cause. Deaths from progressive disease will be stratified as related to CNS progression, related to systemic progression, or both.

8A

3. **Safety:** Safety will be evaluated according to the National Cancer Institute Common Terminology Criteria for Adverse Events (NCI CTCAE) version 4.0^{27} safety will be determined by the number of treatment-related toxicities of > grade 3 severity by CTCAE Version 4.0.

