4.9 Subject Withdrawal/Discontinuation Criteria

Subjects may withdraw consent at any time for any reason or be dropped from the trial at the discretion of the investigator should any untoward effect occur. In addition, a subject may be withdrawn by the investigator or the Sponsor if enrollment into the trial is inappropriate, the trial plan is violated, or for administrative and/or other safety reasons. Specific details regarding discontinuation or withdrawal are provided in Section 7.1.4 – Other Procedures.

A subject must be discontinued from the trial for any of the following reasons:

- The subject or legal representative (such as a parent or legal guardian) withdraws consent.
- CNS progression (as detailed in Table 8)
- Unacceptable adverse experiences as described in Section 6.2.
- Intercurrent illness that prevents further administration of treatment
- Investigator's decision to withdraw the subject
- The subject has a confirmed positive serum pregnancy test
- Noncompliance with trial treatment or procedure requirements
- The subject is lost to follow-up

• Completed 24 months of uninterrupted treatment with pembrolizumab or 35 administrations of study medication, whichever is later.

Note: 24 months of study medication is calculated from the date of first dose. Subjects who stop pembrolizumab after 24 months may be eligible for up to one year of additional study treatment if they progress after stopping study treatment.

Administrative reasons

The End of Treatment and Follow-up visit procedures are listed in Section 5.0 (Trial Flow Chart). After the end of treatment, each subject will be followed for 30 days for adverse event monitoring (serious adverse events will be collected for 90 days after the end of treatment as described in Section 6.1.5.1). Subjects who discontinue for reasons other than progressive disease will have post-treatment follow-up for disease status until disease progression, initiating a non-study cancer treatment, withdrawing consent or becoming lost to follow-up. After documented disease progression each subject will be followed by telephone for overall survival until death, withdrawal of consent, or the end of the study, whichever occurs first.

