7.2.5. Secondary Efficacy Endpoints

1. CNS Progression-Free Survival (PFS)

PFS is defined as the time from first day of study treatment until date of progression. Progression will be stratified into CNS progression (radiologic or cytology or clinical). CNS radiologic progression will be assessed by MRI criteria, CNS cytologic progression will be determined pathologically, and neurologic progression will be determined as per section 6.1.2.7 and Table 8 respectively. PFS will be calculated using the Kaplan-Meier method.

2. Overall Survival

Overall survival will be defined as the date of study entry until date of death from any cause. Cause of death will be recorded.

3. Safety

The primary safety objective of this trial is to characterize the safety and tolerability of pembrolizumab in subjects with LMD. The primary safety analysis will be based on subjects who experienced toxicities as defined by CTCAE, Version 4.0 criteria (Appendix 2). The attribution to drug, time-of-onset, duration of the event, its resolution, and any concomitant

medications administered will be recorded. AEs will be analyzed including but not limited to all AEs, SAEs, fatal AEs, and laboratory changes. Furthermore, specific immune-related adverse events (irAEs) will be collected and designated as immune-related events of clinical interest (ECIs) as described in Section 6.2.3.2

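### Section 6.1.2.7 lists persistently positive CSF cytology under both Improved and Progression, so a patient who is not worsening can be counted as a CNS-PFS event

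*Combined protocol and SAP*

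**What the plan says.** Section 6.1.2.7 grades CNS response on four levels, first in Table 8 and then in prose. The prose takes positive cytology to mean "either detectable malignant cells in the CSF, or a pathology read that is reported as" suspicious. It attaches no cell-count threshold. Three sentences then use the CSF result:

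- Improved includes "a 50% decrease in CSF tumor cells or persistent positive CSF cytology as defined above".
- For Stable: "Patients with stable disease will be defined as less than 50% improvement in number of CSF tumor cells". The sentence ends by requiring that nothing points to progression.
- For Progression: "Progression will be defined as more than 25% increase in the number of tumor cells or persistent positive CSF cytology as defined above". Larger masses and new neurologic signs are further alternatives.

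In Table 8, a patient who is clinically improved or clinically stable but has progression on MRI or CSF is graded as progressed overall. The first of these rows reads "Improved Progression Progression".

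Section 4.1.5.1.2 makes cytologic progression a CNS-PFS event in its own right. It describes it as "cytologic (determined by pathologic assessment of CSF cytology including cell count, differential, glucose" and refers to 6.1.2.7. Section 7.2.5 says "CNS cytologic progression will be determined pathologically", in a sentence that also cites 6.1.2.7 and Table 8. Section 4.9 lists "CNS progression (as detailed in Table 8" among the reasons for which a subject must be discontinued.

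**The concern.** Inclusion 4B in section 4.2.6 admits patients on positive cytology. For them, a later positive result is the finding they came in with. Taken alone it shows no change, and it is compatible with a falling cell count. A progression endpoint should record worsening. If persistence counts as progression, CNS-PFS partly records failure to clear the CSF.

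Two further consequences follow. Clinical improvement alone counts as response on the primary endpoint (4.1.5.1.1 and 7.2.4), so one patient could be a primary-endpoint responder and a CNS-PFS event at the same visit. And because the same result also appears under Improved, two assessors could grade identical data in opposite directions and both be following the text.

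**Working it through.** **Inputs.** Analyzable patients: 16 (section 7.2.1). The plan's own inflation reproduces: 16 / (1 − 0.10) = 17.8, rounded up to 18. The plan gives no figure for the CSF-positive share at baseline or for expected clearance, so both are assumptions here. Section 4.1.4.4 cites cytology clearance of 9/14 = 64% and 1/11 = 9% with two other drugs. That leaves 36% to 91% still positive, and I use it only to set a range.

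**Step 1: trace one patient.** Take a patient who is CSF-positive at baseline and on study, with an unchanged cell count and stable neurologic function.

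| Sentence applied to the CSF result | Met? | Table 8 result (clinically stable) |
|---|---|---|
| Improved | Yes, by persistence | Improved |
| Stable | Count band met (0% is less than 50%), but only if not progressed | Stable |
| Progression | Yes, by persistence | Progression |

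One set of data reaches three grades. The Stable sentence yields to progression, and Table 8 lets Progression in the MRI/CSF column override a stable or improved clinical assessment. The natural reading is therefore Progression. A 40% fall in tumor cells with improved neurologic function ends in the same place: the Stable count band is met, the Progression wording is also met, and Table 8 grades clinically improved plus progression as Progression.

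**Step 2: timing.** Cycles last 3 weeks (Table 4). Section 6.1.2.8.3 places the first on-study sample before cycle 3, at about 2 × 3 = 6 weeks. The next scheduled sample is 2 to 3 weeks after cycle 4 is given, at about 9 + 2 to 9 + 3 = 11 to 12 weeks, or before cycle 5. If a positive baseline plus one on-study positive is persistence, the event falls at about week 6. If two on-study positives are needed, it falls at the later sample. The condition of at least two cycles in the Progression sentence, even if it covers cytology, does not protect the week-6 sample, which already follows two cycles.

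**Step 3: number of patients.** Assume that 8 of 16 are CSF-positive at baseline.

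- Low: 8 × 0.36 = 2.9, about 3.
- High: 8 × 0.91 = 7.3, about 7.

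These counts assume that all are event-free until the sample.

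**Step 4: effect on the median, week-6 reading.** Assume exponential CNS-PFS with true median m weeks, and persistence unrelated to the true event time. Then S(6) = 0.5^(6/m). If a share r of event-free patients is scored as progressed at week 6, the Kaplan-Meier median falls to week 6 once S(6) × (1 − r) ≤ 0.5, that is r ≥ 1 − 0.5/S(6). Step 3 implies r between 0.5 × 0.36 = 0.18 and 0.5 × 0.91 = 0.455. Where the threshold is not reached, the median is 6 + m × log2[S(6)(1 − r)/0.5].

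| True median | S(6) | Threshold r | Median at r = 0.18 | Median at r = 0.455 |
|---|---|---|---|---|
| 12 weeks | 0.707 | 29% | 8.6 | 6 |
| 18 weeks | 0.794 | 37% | 12.8 | 6 |
| 26 weeks | 0.852 | 41% | 18.6 | 6 |

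**The case against.** The best reply is that the paragraph does not settle the matter. The phrase sits under Improved as well, no sentence says which category prevails, and persistence is undefined. Cytologic response needs two consecutive negative samples, and section 6.1.5.3.3 speaks of confirmed CNS progression, so a requirement for two on-study positives is a fair reading. All of this stands. A reader might infer that every CSF-positive patient who is stable becomes an event at the first on-study sample, but the documents do not support so flat a statement. The uncertainty does not rescue the rule, because a progression criterion that also qualifies as improvement cannot be applied consistently.

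A reader might also infer that median CNS-PFS would sit near 6 weeks whatever the drug does. That fails. If 5 of 16 (31%) were scored at week 6 with a true median of 18 weeks, 0.79 × 0.69 = 0.55 would remain event-free, so the median would not be at week 6. Nor should the Table 1 response rates stand in for CSF clearance, since most are composites. The 0% entries, for example, required clinical, radiologic and cytologic response together.

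Sections 4.1.5.1.2 and 7.2.5 might be taken for rival definitions. Both refer to 6.1.2.7, so they are loose wording that needs alignment.

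Finally, CNS-PFS is secondary and Table 12 disclaims formal inference. That limits the consequence to a descriptive curve, but the curve would still be misread.

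**Conclusion.** The concern holds as an internal contradiction with a damaging natural reading. Persistently positive CSF, with no increase in cells, meets the wording of both Improved and Progression. Table 8 and the condition in the Stable sentence push it to Progression, and hence into CNS-PFS.

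The size depends on assumptions that the documents do not fix. With half of 16 patients CSF-positive at baseline and 36% to 91% of those still positive, about 3 to 7 would be scored as progressed on this criterion alone. At the low end the week-6 median thresholds of 29%, 37% and 41% are not reached, though the median is shortened. At the high end all three are exceeded. Only patients CSF-positive at baseline are affected. The median calculation applies only if one on-study positive is enough.

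A reader might go further and conclude that these patients are necessarily discontinued before the 12-week primary assessment. That follows only on the week-6 reading. What the documents do show is that 4.9 relies on the same contradictory classification.

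**What to change.** For the CNS-PFS endpoint:

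1. In 6.1.2.7, remove persistent positivity as a stand-alone criterion from both the Progression and the Improved sentences. Removing it from Progression alone would leave unchanged positive CSF both Stable and Improved. Table 8 would then grade a clinically stable patient as Improved, although 4.1.5.1.1 requires conversion to negative for cytologic response.
2. Let cytologic progression rest on the threshold already in the text, a rise of more than 25% in tumor cells. State that persistently positive CSF without that rise is not a CNS-PFS event.
3. Make the categories mutually exclusive.
4. Align the parenthesis on count, differential and glucose in 4.1.5.1.2, and the word pathologically in 7.2.5, with that one rule.

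The cost is wording, with no new samples or visits. The downside is that fewer early cytologic events are counted.

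Section 4.9 discontinues on Table 8 progression, so a change to the endpoint definition touches it. The sponsor must reconcile 6.1.2.7, Table 8 and 4.9. No rule for stopping treatment is proposed here.

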After completion of 4 cycles of therapy, subjects will be evaluated every 6-9 weeks with radiologic imaging of the body (CT) and CNS (MRI) to assess response to treatment both inside and outside of the CNS. Response assessments will be completed by a radiologist at the treating site, findings will be confirmed by an independent radiologist, and evaluated by RECIST 1.1 criteria and immune-related criteria (irRC) for systemic disease, and MRI criteria for CNS disease. Following the first radiologic assessment of the body that demonstrates radiologic progressive disease (PD), RECIST 1.1 will be adapted as described in section 6.1.2.7.5 (Table 9) to accommodate for the tumor response patterns seen with pembrolizumab treatment (e.g., tumor flare) using immune-related RECIST criteria. Contrast-enhanced MRI Brain scans will be used to assess for measurable disease in the CNS at the time of screening, and to determine CNS radiologic response during the study. CNS radiologic response by MRI will be defined as a reduction in size of a measurable lesion throughout the neuro-axis, where a measurable lesion will be defined as one that is greater than or equal to 3mm in size, as detailed in section 6.1.2.7. CNS cytologic response will be assessed by two serial CSF cytology samples, as detailed in the section 6.1.2.8.3. Clinical response will be evaluated by the treating investigator, detailed in section 6.1.2.7 (Table 8).

[figure not shown]
After completion of 4 cycles of therapy or the patient's last dose of therapy, each subject will be followed for 90 days after the end of treatment for adverse event monitoring, or 30 days after the end of treatment if the subject initiates new anti-cancer therapy. Subjects who discontinue treatment for reasons other than PD will have post-treatment follow-up for disease status until PD, initiation of a new cancer therapy, withdrawal of consent, or becoming lost to follow-up. All subjects will be followed by telephone contact for overall survival (OS) until death, withdrawal of consent or the Investigator is notified by the Sponsor to discontinue follow-up, whichever comes first.

This trial will be conducted in conformance with Good Clinical Practices.

Specific procedures to be performed during the trial, as well as their prescribed times and associated visit windows, are outlined in the Trial Flow Chart – Section 5.0 Details of each procedure are provided in Trial Procedures- Section 6.0.

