6.1.2.7.5 Immune-related RECIST

RECIST 1.1 will be adapted to account for the unique tumor response characteristics seen with treatment of pembrolizumab. Immunotherapeutic agents such as pembrolizumab may produce anti-tumor effects by potentiating endogenous cancer-specific immune responses. The response patterns seen with such an approach may extend beyond the typical time course of responses seen with cytotoxic agents, and cam manifest a clinical response after an initial increase in tumor burden or even the appearance of new lesions. RECIST may not provide an accurate response assessment of immunotherapeutic agents such as pembrolizumab. Immune-related RECIST (irRECIST) is RECIST 1.1 adapted as described below to account for the unique tumor response seen with immunotherapeutics. Following site identification of PD, irRECIST will be used by site investigators to assess tumor response and progression and make treatment decisions.

If radiologic imaging by the site identifies PD by RECIST 1.1, imaging should be repeated >4 weeks later in order to confirm PD with the option of continuing therapy per below while awaiting radiologic confirmation of progression.

If repeat imaging shows <20% tumor burden compared to nadir, stable or improved previous new lesion (if identified as cause for initial PD), and stable/improved non-target disease, if identified as cause of initial PD), PD is not confirmed. Treatment may continue and subsequently follow the regular imaging schedule.

If repeat imaging confirms PD (irPD) due to any of the scenarios listed below, this will be recorded. However, pembrolizumab may be continued in patients if they have not demonstrated CNS progression, as detailed in Table 8, at the discretion of the treating investigator.

If determining whether or not the tumor burden has increased or decreased, site study team should consider all target lesions as well as non-target lesions.

Scenarios where PD is confirmed at repeat imaging:

- Tumor burden remains >20% and at least 5mm absolute increase compared to nadir
- Non-target disease resulting in initial PD is worse (qualitative)
- New lesion resulting in initial PD is worse (qualitative)
- Additional new lesion(s) since last evaluation
- Additional new non-target progression since last evaluation

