6.1.5.3.3. Survival Follow-up

Once a subject experiences confirmed CNS progression or starts a new anti-cancer therapy, the subject moves into the survival follow-up phase and should be contacted by telephone every 12 weeks to assess for survival status until death, withdrawal of consent, or the end of the study, whichever occurs first.

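### CNS progression has no MRI growth margin and a bare 25% CSF cell-count rule, so measurement error alone can create CNS-PFS events in stable patients

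*Combined protocol and SAP*

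**What the plan says.** The progression rule is in the text under Table 8 in section 6.1.2.7. Its CSF part reads: "Progression will be defined as more than 25% increase in the number of tumor cells", with persistently positive cytology as the alternative. Its MRI part is "an increase in size of LMD masses on radiologic assessment". The third route is new neurologic signs or symptoms.

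The MRI part gives no percentage and no millimetre minimum. It does not say whether the comparison is with baseline or nadir. By contrast, MRI improvement needs "a 50% shrinkage in the bidirectional measurements of leptomeningeal disease". The stable category begins "Patients with stable disease will be defined as less than 50% improvement in number of CSF tumor cells"; for MRI it mentions only a reduction in size and gives no band for small growth. Section 2.1 makes a lesion measurable when it is "greater than or equal to 3mm in size".

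In Table 8 a clinically stable or improved patient with progression on MRI or CSF is scored as progression overall. Section 4.1.5.1.2 makes radiologic or cytologic progression alone a CNS-PFS event and lists cell count in the cytologic assessment. Section 7.2.5 refers back to 6.1.2.7 and Table 8.

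For systemic disease, section 6.1.2.7.5 requires repeat imaging, and one criterion for confirming progression is "Tumor burden remains >20% and at least 5mm absolute increase compared to nadir". Section 6.1.5.3.3 starts survival follow-up with the words "Once a subject experiences confirmed CNS progression", but no section says how CNS progression is confirmed. Section 4.9 requires discontinuation on CNS progression as in Table 8.

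**The concern.** A threshold of zero on a measured quantity turns part of the reading noise into events. At the 3 mm cut-off, one extra millimetre in one diameter takes the product from 3 x 3 = 9 to 3 x 4 = 12, a 33% rise. The CSF threshold has a percentage but no minimum count or fixed counting volume, and section 4.1.5.2.1 itself warns of low cellularity.

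At stake is the meaning of CNS-PFS. The trial has one arm and 16 analyzable patients (section 7.2.1), so there is no control curve carrying the same error, and a few spurious early events would visibly lower the Kaplan-Meier curve. Because 4.9 uses the same definition to end treatment, a spurious call may also change what happens to the patient.

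**Working it through.** **Inputs from the documents.** MRI rule: any increase. CSF rule: more than 25%. Two scheduled on-treatment assessments, after cycles 2 and 4 (section 2.1). Smallest measurable lesion 3 mm. 16 analyzable patients. The plan states no figure for reading error, lesion number, CSF cell count or CNS-PFS, so there is no plan figure to reproduce.

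**Assumptions.** Disease truly unchanged; independent errors at baseline and two follow-ups; comparison with baseline; normal reading error with SD 0.25, 0.5 or 1.0 mm; Poisson counting error for CSF on equal volumes.

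**MRI, unrounded readings.** The three readings are exchangeable, so baseline is the largest with probability 1/3. The chance that at least one follow-up exceeds it is 1 - 1/3 = 2/3, whatever the SD.

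**MRI, whole-millimetre readings, one diameter, SD 0.5 mm.** The reading equals the true value with probability 0.683 and is 1 mm above or below with probability 0.157 each.
- One follow-up: P(tie) = 0.683² + 2 x 0.157² = 0.516, so P(increase) = (1 - 0.516)/2 = 0.24.
- Either of two: 1 - Σ P(b) P(X ≤ b)², summed over baseline readings b. The sum is 0.004 + 0.483 + 0.157 + 0.001 = 0.645, giving 0.35.

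**MRI, whole-millimetre readings, product of two diameters** (simulation, 400,000 patients per setting, either of two follow-ups, one 5 mm lesion):

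| Reading SD | Any increase in product |
|---|---|
| 0.25 mm | 12% |
| 0.5 mm | 49% |
| 1.0 mm | 60% |

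If all 16 analyzable patients had one such lesion and both scans, the expected false events would be 16 x 0.12 = 1.9, 16 x 0.49 = 7.8 and 16 x 0.60 = 9.6. This is an upper illustration: patients may enter on cytology alone, and not all will reach the second scan or have unchanged disease.

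**CSF, unchanged burden.** For mean count μ, P(either of two samples) = Σ Pois(x; μ)[1 - F(1.25x)²] over baseline counts x ≥ 1, where F is the Poisson distribution function.

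| Mean count | One sample | Either of two |
|---|---|---|
| 10 | 30% | 44% |
| 50 | 13% | 21% |
| 100 | 6% | 10% |
| 200 | 1% | 2% |

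At a mean of 50, the SD of a difference between two counts is √100 = 10, so a 25% rise (12.5 cells) is only 1.25 SD.

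**An example margin.** Require more than 25% in the summed product and at least 2 mm in a diameter; whole-millimetre readings, either of two follow-ups:

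| Lesion size, SD | One lesion | Three lesions |
|---|---|---|
| 5 mm, 0.5 mm | 7% | 5% |
| 3 mm, 0.5 mm | 9% | 12% |
| 5 mm, 1.0 mm | 31% | 27% |
| 3 mm, 1.0 mm | 35% | 40% |

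Without a margin, three 5 mm lesions at SD 0.5 mm give 60% if the summed product is scored and 86% if a rise in any one lesion counts. The like-for-like gain from the margin is therefore 60% to 5%.

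**The case against.** A sensible radiologist would call a trivial change stable. Table 8 has a stable category, section 2.1 adds an independent radiologist, and section 6.1.2.7 requires the same imaging technique throughout. This stands in part. A reader might infer that two thirds of stable patients will be scored as progressed whatever the error. The documents do not support that: the figure needs every sub-resolution difference to be scored as growth. But no tolerance is written, two readers could code the same scan differently, and re-reading one scan does not remove scan-to-scan variation.

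The size is also uncertain. With small error and rounding, or with counts of 200 or more, the problem is minor. CNS-PFS is a secondary endpoint, summarised by Kaplan-Meier without formal inference. All of this stands and limits the weight of the point.

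A reader might think the irRECIST repeat-imaging step already covers the CNS. It adapts RECIST 1.1, which section 6.1.2.7.4 confines to disease outside the CNS.

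A reader might also infer a known bias in the primary response rate. Table 8 does let progression override clinical improvement, but section 7.2.4 scores response on the most easily assessed criterion, so neither the direction nor the size of any effect can be derived.

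Finally, section 6.1.2.7.2 says that no standard radiologic criteria for LMD exist. That is a reason to justify a margin from data; it does not justify having none.

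**Conclusion.** The point holds for CNS-PFS. The written rule scores any MRI growth, and any CSF count rise above 25%, as progression, and gives LMD neither the margin nor the repeat imaging that systemic disease receives. Error alone can therefore create events in stable patients. That conclusion rests on the text.

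The size rests on assumption: about 12% to 60% per unchanged lesion over two scans for reading SDs of 0.25 to 1.0 mm, 67% in the limiting unrounded case, and about 44% down to 2% for CSF mean counts of 10 to 200.

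One related defect needs no measurement error. Persistent positive cytology appears under both the improved and the progression definitions, so an unchanged positive result can be read as an event.

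**What to change.** For CNS-PFS scoring only:

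- **MRI.** Name the reference scan. Require a relative and an absolute increase in the summed bidirectional product, for example more than 25% together with at least 2 mm in a diameter. Set the final margin from the readers' own repeatability, because this example still leaves about 27% to 40% at SD 1 mm for 3 to 5 mm lesions.
- **CSF.** Count a rise only when it exceeds counting error on equal volumes, or count conversion from negative to positive. Do not simply drop the count rule and keep the rest: that would leave unchanged positive cytology as progression. Remove it as a progression event and resolve its place under two categories.
- **Confirmation.** Define the term used in section 6.1.5.3.3.

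The statistical cost is that true small growth is dated slightly later. There is also an operational cost. Section 6.1.2.7.2 ends imaging at Table 8 CNS progression, so a patient stopped under Table 8 without meeting the endpoint margin would have no later scan. The plan must say how that patient is scored.

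The clinical team must reconcile sections 4.9, 6.1.2.7 and 6.1.5.3.3 on discontinuation, the progression definition and confirmation. No treatment rule is proposed here.
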